10 ADVERSE EVENTS: LIST AND REPORTING REQUIREMENTS

10.1 Safety Parameters and Definitions

Safety assessments will consist of monitoring and recording adverse events, including serious adverse events and non-serious adverse events of special interest; measurement of protocol-specified safety laboratory assessments; measurement of protocol-specified vital signs; and other protocol-specified tests that are deemed critical to the safety evaluation of the study. Assessment will occur per protocol. Certain types of events require immediate reporting to the Principal Investigator, as outlined in [**Section 10.4**](#).

A comprehensive list of all reported adverse events and any potential risks associated with atezolizumab, carboplatin, and etoposide can be found in the manufacturer's package insert for each agent.

10.2 Definitions

Adverse Event:

An adverse event (AE) is any untoward or unfavorable medical occurrence in a human subject, including abnormal sign, symptom or disease, temporally associated with the subject's participation in research, whether or not considered related to the subject's participation in the research. Abnormal results of diagnostic procedures are considered to be adverse events if the abnormality:

- results in study withdrawal
- is associated with a serious adverse event
- is associated with clinical signs or symptoms
- leads to additional treatment or to further diagnostic tests
- is considered by the investigator to be of clinical significance

**Columbia University Irving Medical Center
Herbert Irving Comprehensive Cancer Center
CUMC IRB – AAAT0174**

AE could also be a Pre Existing medical condition (other than the condition being studied) judged by the investigator to have worsened in severity or frequency or changed in character during the protocol-specified AE reporting period.

Serious Adverse Event:

Adverse events are classified as serious or non-serious. A serious adverse event (SAE) is any AE that is:

- Death(i.e., the AE actually causes or leads to death).
- life-threatening (i.e., the AE, in the view of the investigator, places the subject at immediate risk of death. It does not include an AE that, had it occurred in a more severe form, might have caused death).
- requires inpatient hospitalization/prolongation of existing hospitalization, unless:

**Columbia University Irving Medical Center
Herbert Irving Comprehensive Cancer Center
CUMC IRB – AAAT0174**

- routine treatment or monitoring of the studied indication, not associated with any deterioration in condition (procedures such as central line placements, paracentesis, pain control)
- elective or pre-planned treatment for a pre-existing condition that is unrelated to the indication under study and has not worsened since the start of study drug
- treatment on an emergency outpatient basis for an event not fulfilling any of the definitions of an SAE given above/below and not resulting in hospital admissions
- social reasons and respite care in the absence of any deterioration in the patient's general condition
- results in persistent or significant disability or incapacity (i.e., the AE results in substantial disruption of the subject's ability to conduct normal life functions)
- a congenital anomaly or birth defect
- an important medical event

Important medical events are those that may not be immediately life threatening, but are clearly of major clinical significance. They may jeopardize the subject, and may require intervention to prevent one of the other serious outcomes noted above. For example, drug overdose or abuse, a seizure that did not result in in-patient hospitalization or intensive treatment of bronchospasm in an emergency department would typically be considered serious.

All adverse events that do not meet any of the criteria for serious events should be regarded as non-serious adverse events.

Serious adverse events are required to be reported by the investigator to the Sponsor immediately (i.e., no more than 24 hours after learning of the event; see Section 10.4 for reporting instructions).

Unanticipated Problem:

An unanticipated problem is any incident, experience or outcome involving risks to subjects or others in any human subjects research that meets all of the following criteria:

- Unexpected (in terms of nature, severity or frequency) given (a) the research procedures that are described in the IRB-approved protocol and informed consent document, and (b) the characteristics of the subject population being studied;
- Related or possibly related to participation in such research (e.g., there is a reasonable possibility that the incident, experience or outcome may have been caused by the procedures involved in such research); and
- Suggests that the research places subjects or others at a greater risk of harm (including physical, psychological, economic or social harm) than was previously known or recognized.

Adverse Event of Special Interest (AESI)

AESIs are a subset of Events to Monitor (EtMs) of scientific and medical concern specific to the product, for which ongoing monitoring and rapid communication to the Principal Investigator is required. Such an event might require further investigation in order to characterize and understand it. Depending on the nature of the event, rapid communication by the Principal Investigator to other parties (e.g., Regulatory Authorities) may also be warranted.

**Columbia University Irving Medical Center
Herbert Irving Comprehensive Cancer Center
CUMC IRB – AAAT0174**

The following AEs are considered of special interest and must be reported to the Principal Investigator expeditiously, irrespective of regulatory seriousness criteria:

The following confirmed treatment-emergent autoimmune conditions:

- Systemic lupus erythematosus
-
- Nephritis
- Ocular toxicities (e.g., uveitis, retinitis, optic neuritis)
- Grade \geq 2 cardiac disorders (e.g., atrial fibrillation, myocarditis, pericarditis)
- Vasculitis
- Autoimmune hemolytic anemia.
- Severe cutaneous reactions (e.g., Stevens-Johnson syndrome, dermatitis bullous, toxic epidermal necrolysis)
- Events suggestive of hypersensitivity, cytokine release syndrome, infusion-related reactions, macrophage activating syndrome, hemophagocytic lymphohistiocytosis
- Cases of potential drug--induced liver injury that include an elevated ALT or AST in combination with either an elevated bilirubin or clinical jaundice, as defined by Hy's law
 - Treatment-emergent ALT or AST \geq 3x ULN in combination with total bilirubin \geq 2x ULN
 - Treatment-emergent ALT or AST \geq 3x ULN in combination with clinical jaundice
- Data related to a suspected transmission of an infectious agent by the study drug (STIAMP), as defined below:

Any organism, virus, or infectious particle (e.g., prion protein transmitting transmissible spongiform encephalopathy), pathogenic or non-pathogenic, is considered an infectious agent. A transmission of an infectious agent may be suspected from clinical symptoms or laboratory findings that indicate an infection in a patient exposed to a medicinal product. This term applies only when a contamination of the study drug is suspected.

Adverse Event Reporting Period

The study period during which AEs and SAEs where the patient has been exposed to Genentech product must be reported during the reporting period which begins after informed consent is obtained. Subjects will be followed for serious adverse events and adverse events of special interest for 90 days after their last dose of study drug or initiation of new anti-cancer therapy, whichever occurs first. For all other adverse events, Subjects will be followed for 30 days after their last dose of study drug or initiation of new anti-cancer therapy, whichever occurs first. Investigators are instructed to report all SAEs and AESIs considered related to study treatment regardless of time after study.

Post-study Adverse Event

Subjects who have an ongoing study treatment-related adverse event upon study completion or at discontinuation from the study will be followed until the event has resolved to baseline grade, the event is assessed by the investigator as stable, new anti-cancer treatment is initiated, the patient is lost to follow-up, the patient withdraws consent, or it has been determined that study treatment or participation is not the cause of the adverse event. At the last scheduled visit, the investigator should instruct each subject to report any subsequent event(s) that the subject or the treating physician believes might reasonably be related to participation in this study.

PROCEDURES FOR ELICITING, RECORDING, AND REPORTING ADVERSE EVENTS

Eliciting Adverse Events

A consistent methodology for eliciting AEs at all subject evaluation time points should be adopted. Examples of non-directive questions include:

- “How have you felt since your last clinical visit?”
- “Have you had any new or changed health problems since you were last here?”

Specific Instructions for Recording Adverse Events

Investigators should use correct medical terminology/concepts when reporting AEs or SAEs. Avoid colloquialisms and abbreviations.

Diagnosis vs. Signs and Symptoms

If known at the time of reporting, a diagnosis should be reported rather than individual signs and symptoms (e.g., record only liver failure or hepatitis rather than jaundice, asterixis, and elevated transaminases). However, if a constellation of signs and/or symptoms cannot be medically characterized as a single diagnosis or syndrome at the time of reporting, it is acceptable to report the information that is currently available. If a diagnosis is subsequently established, it should be reported as follow-up information.

Baseline/Preexisting Condition

A baseline/preexisting condition is one that is present at the start of the study. A preexisting condition should be recorded as an adverse event if the frequency, intensity, or if the character of the condition worsens during the study period.

General Physical Examination Findings

At screening, any clinically significant abnormality should be recorded as a preexisting condition. At the end of the study, any new clinically significant findings/abnormalities that meet the definition of an adverse event must also be recorded and documented as an adverse event.

Abnormal Laboratory Values

A clinical laboratory abnormality should be documented as an adverse event if any one of the following conditions is met:

- The laboratory abnormality is not otherwise refuted by a repeat test to confirm the abnormality
- The abnormality suggests a disease and/or organ toxicity

- The abnormality is of a degree that requires active management (e.g., change of dose, discontinuation of the drug, more frequent follow-up assessments, further diagnostic investigation, etc.).

Hospitalization, Prolonged Hospitalization or Surgery

Any adverse event that results in hospitalization or prolonged hospitalization should be documented and reported as a serious adverse event unless specifically instructed otherwise in this protocol. Any condition responsible for surgery should be documented as an adverse event if the condition meets the criteria for an adverse event.

Neither the condition, hospitalization, prolonged hospitalization, nor surgery are reported as an adverse event in the following circumstances:

- Hospitalization or prolonged hospitalization for diagnostic or elective surgical procedures for a preexisting condition. Surgery should **not** be reported as an outcome of an adverse event if the purpose of the surgery was elective or diagnostic and the outcome was uneventful.
- Hospitalization or prolonged hospitalization required to allow efficacy measurement for the study.
- Hospitalization or prolonged hospitalization for therapy of the target disease of the study, unless it is a worsening or increase in frequency of hospital admissions as judged by the treating investigator.

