9.5 Radiation Dose Modification

We will assess the rate of liver SBRT-specific toxicities in excess of those expected from atezolizumab + chemotherapy. If >3 patients (~20% of projected enrollment) require replacement, enrollment will be paused for the study team to review safety data until that point to assure safe continuation of the study.

Specifically, toxicities of special interest will include those anatomically relevant to the radiation field, including but not limited to: dysfunction, pain, inflammation, obstruction, stenosis, ulceration, perforation, hemorrhage, necrosis, or vasculopathy of the alimentary or hepatopancreaticobiliary tracts. Excess irAEs will also be investigated as possibly related to study combination therapy.

If it is determined that excess toxicity is resulting from the study combination, enrollment may resume at an SBRT dose reduction from 10 to 6 Gy per dose. After dose-reduction, if an additional patient requires replacement due to toxicity, we will again pause enrollment for safety review. An additional dose-reduction to 4 Gy per dose may then be considered. If further toxicity of special interest is observed we will close the study.

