12 STUDY CALENDAR

		Every 3 week cycles (± 2 days)						
Procedure/Intervention ^a	Screening	Induction Phase				Maintenance Phase	Treatment Discontinuation Visit	Survival Follow up
	Days -28 to -1	C1D 1	C2D 1	C3D 1	C4D 1	CXD1	<30 days after last dose	Every 3 months
Informed Consent	X							
Tumor Biopsy ^b	X							
Liver metastasis biopsy ^c	X							
Clinical Assessments								
Medical and Cancer History	X							
Physical Examination	X	X	X	X	X	X	X	
ECOG performance status	X	X	X	X	X	X	X	
Vital signs	X	X	X	X	X	X	X	
12 Lead ECG	X							
Concomitant Medications	X	X	X	X	X	X	X	
Adverse Events ^d			X	X	X	X	X	
Survival Status ^e								X
Treatment								
Atezolizumab ^f		X	X	X	X	X		
Carboplatin ^g		X	X	X	X			
Etoposide ^g		X	X	X	X			
Liver-directed radiation ^h			X					
Tumor Assessments								
Optional tumor biopsy		At time of progression						
Brain MRI or CT head w/ contrast	X							
CT chest and abdomen w/ contrast ⁱ	X ^j				X	X ^k	X	X ^l
PET/CT (if applicable)	X							
Laboratory Assessments^m								
CBC	X	X	X	X	X	X	X	
Chemistry ⁿ	X	X	X	X	X	X	X	
PT/PTT	X							
TSH, free T3, free T4 ^o	X	X			X	X	X	
Urinalysis	X						X	
Serum beta-HCG ^p	X	X						
EBV, HIV, HCV, HBV serology ^q	X							
Research bloods ^r	X _{s,t}	X ^t	X ^t	X ^t	X ^t	X ^t	X ^t	

**Columbia University Irving Medical Center
Herbert Irving Comprehensive Cancer Center
CUMC IRB – AAAT0174**

1. Assessments should be performed prior to study drug infusion
2. Histologic confirmation of SCLC diagnosis
3. Liver biopsy must be obtained prior to pre-treatment for evaluation of exploratory biomarkers
4. All serious adverse events and adverse events of special interest, regardless of relationship to study drug, will be reported until 90 days after the last dose of study drug or initiation of new anti-cancer therapy, whichever occurs first. All other adverse events, regardless of relationship to study drug, will be reported until 30 days after the last dose of study drug or initiation of new anti-cancer therapy, whichever occurs first. After this period, the investigator should report any serious adverse events or adverse events of special interest believed to be related prior to study drug treatment.

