- In-field local control will be defined as the absence of disease progression within the planning target volume (PTV) as per RECIST v1.1 on CT at 6 months following radiation treatment
- Out of field disease progression will be defined as the development of lesions outside the PTV as assessed by RECIST v1.1 criteria at 6 months following radiation treatment

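### Adverse-event collection runs from the last drug dose, not from SBRT, so active collection of new, late, non-serious SBRT toxicity depends on how long the drugs continue

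*Combined protocol and SAP*

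**What the plan says.** Section 10.2 sets two windows, and both end early if new anti-cancer therapy starts. For serious events and AESIs: "Subjects will be followed for serious adverse events and adverse events of special interest for 90 days after their last dose of study drug". For everything else: "For all other adverse events, Subjects will be followed for 30 days after their last dose of study drug or initiation of new anti-cancer therapy". Footnote 4 of the Section 12 calendar repeats the second rule: "All other adverse events, regardless of relationship to study drug, will be reported until 30 days after the last dose of study drug". Related SAEs and AESIs must also be reported however late they occur.

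Section 9.5 says of SBRT that "toxicities of special interest will include those anatomically relevant to the radiation field". Its list runs from pain, inflammation and organ dysfunction up to bleeding, perforation and necrosis in the gut, liver, bile ducts or pancreas. The AESI list in Section 10.2 has a different basis: "AESIs are a subset of Events to Monitor (EtMs) of scientific and medical concern specific to the product". The clear overlap is liver injury meeting Hy's law.

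The last adverse-event mark in the calendar is at the treatment discontinuation visit, "<30 days after last dose". The survival follow-up column has none. Section 15.1 assesses SBRT safety by tabulating toxicities by grade, and assesses in-field control "at 6 months following radiation treatment".

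**The concern.** The length of safety observation after SBRT is set by something other than SBRT. A patient who stops the drugs early, through progression or toxicity, is actively observed for a few weeks after radiation. A patient who stays on atezolizumab is observed for months. Toxicity percentages by grade then pool very unequal follow-up, and the shortest follow-up falls on those who stop early or move soonest to another therapy. If some non-serious SBRT effects appear late, they would be missed selectively in that group.

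The benefit and harm of the same intervention also have different horizons: local control is judged 6 months after radiation, while harm is collected for a time that varies by patient. Section 9.5 uses the same toxicities when deciding whether to resume at a reduced SBRT dose or close the study, so their completeness matters for more than the final table.

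**Working it through.** The plan states no figure for follow-up after SBRT, so there is none to reproduce. The check is day arithmetic on the nominal schedule, with C1D1 as day 1.

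**Inputs**
- 21-day cycles; etoposide on days 1 to 3 of cycles 1 to 4 (Section 11.2). C2D1 is day 22.
- SBRT within 3 days either side of C2D1 (Sections 5.2 and 11.2): starts day 19 to 25.
- Three fractions on alternate days (Section 8.2): last fraction is start + 4, so day 23 to 29.
- Collection ends at last study drug dose + 30 days (Section 10.2), if no new therapy has started.

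**Formula:** days of collection after SBRT = (last dose day + 30) − (last fraction day).

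| Last dose | Day | Collection ends | Days after last fraction |
|---|---|---|---|
| C2D1 | 22 | 52 | 23 to 29 |
| C2D3 (etoposide) | 24 | 54 | 25 to 31 |
| C3D1 | 43 | 73 | 44 to 50 |
| C4D1 | 64 | 94 | 65 to 71 |
| C6D1 | 106 | 136 | 107 to 113 |
| C7D1 | 127 | 157 | 128 to 134 |

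**Patient at the median.** Section 3 gives a median PFS of 4.3 months with atezolizumab in patients with liver metastases: 4.3 × 30.44 = day 131. The last dose before that is C7D1, or C6D1 if cycle 7 is held, which gives 107 to 134 days.

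**Other SBRT timing.** Calendar footnote 8 gives a start within 7 (+/-3) days of C2D1. Read as 4 to 10 days after C2D1 (an assumption), SBRT starts on day 26 to 32 and ends on day 30 to 36. A last dose at C2D1 then leaves 52 − 36 = 16 to 52 − 30 = 22 days.

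**SAEs and AESIs.** With a last dose at C2D1 the window ends on day 22 + 90 = 112, which is 83 to 89 days after the last fraction.

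**How common is a cycle 2 stop?** Assume exponential PFS with median 4.3 months. The share progressed or dead by time t is 1 − 2^(−t/4.3). At 5 weeks (1.15 months) this is 17%; at 7 weeks (1.61 months) it is 23%. Whether imaging would find progression before cycle 3 depends on the schedule. Section 5.2 scans every 6 weeks, so near day 43 (+/-7 days). The calendar grid and Section 13.1 put the first re-evaluation at C4D1, when cycle 3 has already been given.

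**The case against.** The short window is an early-stopping case. It needs a last dose in cycle 2, and under the C4D1 scan schedule a patient stopped on imaging would have had cycle 3 and so at least 44 to 50 days. A patient treated to the median has more than three months, and treatment beyond progression (Section 6.5.2) extends it. A reader might infer that SBRT harm is generally collected for only three to four weeks; the arithmetic does not support that.

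The gravest harm is largely covered. Perforation, bleeding or necrosis that is life-threatening, needs hospital admission or is an important medical event is an SAE, and related SAEs have no time limit. Hy's law liver injury is already an AESI. Section 10.2 also tells subjects to report later events that might be related. One AESI bullet is blank in the text available, so an entry may not be visible. All of this stands. What remains is that subject reporting has no visit or recording window attached, and new non-serious events are not actively sought after the cut-off.

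A reader might also infer that Section 10.2 contradicts Sections 8.5 and 18.8 by ending follow-up of ongoing related events at new therapy. It does not: 8.5 concerns patients removed for unacceptable adverse events, and the follow-up to resolution in 18.8 concerns SAEs. The better comparison is Section 10.3, which follows each event to resolution, stabilization or exclusion of a treatment cause and does not stop at new therapy. Section 10.2 lists among its stopping points: "the event is assessed by the investigator as stable, new anti-cancer treatment is initiated, the patient is lost to follow-up".

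Finally, placing ungraded pain or dysfunction on the AESI list would bring expedited reporting to the principal investigator and possibly the manufacturer. That is a fair argument against that form of remedy.

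**Conclusion.** The point holds in a limited form. No adverse-event window is anchored to SBRT, and active collection of new non-serious SBRT toxicity ranges from 23 to 29 days after the last fraction (last dose C2D1) to about 107 to 134 days (treated to the median PFS). It is 16 to 22 days for a C2D1 last dose under the alternative SBRT timing, and shorter whenever new therapy starts first. These figures assume on-schedule cycles.

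A reader might conclude that SBRT toxicity is under-counted and the regimen will look safer than it is. The documents do not establish that, because they give no onset times. If non-serious effects appear within about four weeks, little is lost. If they appear at 2 to 6 months, most would be missed in patients who stop early. The change is worth making because SBRT safety is a stated objective and the remedy is cheap. It does not affect the primary endpoint.

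**What to change.** 1. In Section 10.2, add a separate list of SBRT events taken from Section 9.5, without AESI expedited reporting. Collect them until the later of the existing window and a fixed time after the last SBRT fraction. Six months would match the local-control endpoint in Section 15.1; the sponsor should set the length. Do not end this window at new anti-cancer therapy, but record the start date of that therapy.
2. Add an adverse-event prompt to the existing tumor-assessment and survival contacts in that period. First reconcile the survival contact frequency, which is every 3 months in the calendar heading and every 4 to 6 months in footnote 5.
3. Reconcile the Section 10.2 rule that ends follow-up of ongoing related events at new therapy with Section 10.3, which has no such stop.
4. Reconcile the SBRT timing (Sections 5.2 and 11.2 against calendar footnote 8) and the first-scan timing (Section 5.2 and footnote 11 against the calendar grid and Section 13.1), since both move the observation period.

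The cost is protocol wording, a calendar mark and a little more data collection, with no new visit or procedure. The drawback is harder attribution for events that arise on second-line therapy, which is why its start date should be recorded.
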